6.1 Overall Design and Plan of the Study

This is a multi-centre, randomized, double-blind, placebo-controlled, parallel-group study in subjects with type 2 diabetes mellitus, age \geq 18 years and a HbA1c ranging from 7.0% to below 10.0%.

[figure not shown]
The study consists of 2 week screening period and 2 week single-blind placebo run-in period, 24 week double-blind treatment period and a 2 week follow-up period.

At the end of the placebo run-in period, subjects will attend the site for the randomization visit (RV). Subjects with 75% or higher treatment compliance with the investigational product (placebo) during the placebo run-in period will be randomized to either treatment groups, 20 mg MP-513 (teneligliptin) or placebo once daily, in a 1:1 ratio.

Subjects will have 6 additional visits (at Week 4, 8, 12, 16, 20 and 24) with treatment and will have a follow-up telephone visit at Week 26. The study duration for a subject who completes the study is 30 weeks (2 weeks screening, 2 weeks placebo run-in, 24 weeks treatment, 2 weeks follow-up).

The study period is from [REDACTED] to [REDACTED].

Table 1 Flow Chart

Enrolled subjects will meet all of the inclusion criteria and none of the exclusion criteria.

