6.6 Study Procedures

6.6.1 Schedule of Investigations and Data Collection

A schedule of study procedures and events is provided in Table 2.

Table 2 Schedule of Visits

Period	Scr. Period	Placebo Run-in Period		Double-blind Treatment Period						Follow-up Period
		PV	RV	V1	V2	V3	V4	V5	V6	
Visit	SV	PV	RV	V1	V2	V3	V4	V5	V6	FV
Visiting Windows	Day -28 +/- 3 days	Day -14 +/- 3 days	Day 1	Week 4 +/- 7 days	Week 8 +/- 7 days	Week 12 +/- 7 days	Week 16 +/- 7 days	Week 20 +/- 7 days	Week 24 ⁽⁵⁾ +/- 7 days	Week 26 ⁽⁶⁾ + 14 days
Items										
Obtain written informed consent	X									
Screening/Inclusion/Exclusion criteria evaluation	X	X	X							
Demographics and complete medical history	X ⁽⁷⁾									
Height	X									
Body weight	X		X	X	X	X	X	X	X	
Vital signs ⁽¹⁾	X	X	X	X	X	X	X	X	X	
12-lead ECG	X		X			X			X	
Routine laboratory evaluations: hematology, chemistry, urinalysis	X		X	X	X	X	X	X	X	
Serum pregnancy test ⁽²⁾	X								X	
HbA1c	X	X	X	X	X	X	X	X	X	
Fasting plasma glucose	X	X	X	X	X	X	X	X	X	
Fasting insulin, C-peptide and glucagon			X	X	X	X	X	X	X	
Dispense medication		X	X	X	X	X	X	X		
Return of unused medication			X	X	X	X	X	X	X	
Assessment of adverse events ⁽³⁾ and concomitant medication	X	X	X	X	X	X	X	X	X	X
Hypoglycaemic episodes ⁽⁴⁾	X	X	X	X	X	X	X	X	X	X
Dispense subject diary and glucometer	X									
Subject diary review		X	X	X	X	X	X	X	X	

Scr period: Screening period, SV: Screening visit, PV: Placebo run-in visit, RV: Randomization visit, FV: follow-up visit

(1) Vital signs (sitting blood pressure, pulse rate and body temperature)

(2) The serum pregnancy test will be performed only for female subjects of childbearing potential.

(3) AEs will be collected and reported on the eCRF from the date of informed consent to 14 days after the final dose of the study drug considering the half-life (T1/2) of MP-513.

(4) The occurrence of hypoglycaemic episodes will be recorded continuously throughout the study by a subject diary

(5) These assessments will also be performed at early termination.

(6) Telephone visit

(7) Including physical examination

A description of the subject assessments at each visit is presented below. All the blood and urine sample collected will be sent to central lab [REDACTED] for measurement.

Screening Visit (28 days plus/minus 3 days prior to treatment)

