- Review use of concomitant treatments
- Blood and urine is to be drawn and sent to the central laboratory according to the local procedure for evaluation of haematology, clinical chemistry, urinalysis, HbA1c, FPG, fasting insulin, C-peptide and glucagon
- Evaluation for any AEs including hypoglycaemic episodes experienced by the subjects since last visit
- Review subject diary
- MP-513 or placebo will be dispensed to the subjects. Unused medication has to be returned to the site
- Subjects are to be instructed that they have to return for the next scheduled visit day.

Treatment Visit 6 (Week 24 plus/minus 7 days of treatment/Early termination visit: date of discontinuation* plus 7 days)

*Date of discontinuation is defined as the date of decision of discontinuation for subjects by the investigator.

This visit is the regular **end of treatment visit**. In case of premature termination, the same evaluations have to be performed as **the early termination visit**.

The following observations/procedures are to be performed and checked:

- Vital signs, body weight and ECG
- Review use of concomitant treatments
- Blood and urine is to be drawn and sent to the central laboratory according to the local procedure for evaluation of haematology, clinical chemistry, urinalysis and HbA1c, FPG, fasting insulin, C-peptide and glucagon.
- A serum pregnancy test is to be performed in females with childbearing potential.
- Evaluation for any AEs including hypoglycaemic episodes experienced by the subjects since last visit
- Review and final collection of subject diary
- Unused MP-513 or placebo has to be returned to the site.

Follow-up Visit (Week 26 plus 14 days following completion / Early termination of double-blind treatment period)

Two weeks after end of treatment, a telephone follow-up visit will take place to ask the subjects about any AEs including hypoglycaemic episodes experienced by the subjects since the last visit and use of concomitant treatments.

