Further details will be outlined in the eCRF manual.

Cardiovascular events

An Event Adjudication Committee (EAC) will be set up to evaluate the cardiovascular events.

Cardiovascular events are defined as below: Death; Myocardial Infarction; Hospitalisation for Unstable Angina; Stroke & Transient Ischaemic Attack (TIA) (fatal & non-fatal); Urgent Revascularisation Procedures; Hospitalisation for Heart Failure

The detailed review procedure will be developed in a booklet prior to initiating the trial.

Adverse Events

All AEs that occur during the study from the signing of informed consent form through to 14 days after the final dose of the study drug are to be collected and reported on the eCRF, regardless of whether they are reported by the subject, elicited by investigator questioning, detected through physical examination, or by other means.

As far as possible, each AE is described by:

- duration (start and end dates)
- severity grade (mild, moderate, severe)
- investigator causality assessment (relationship to the study product)
- action taken (change of study medication)
- outcome
- seriousness

Definitions and Handling of Adverse Events

AE

An AE is any untoward medical occurrence (change in anatomical, physiological, metabolic function, or clinically significant laboratory abnormality) in a subject, which does not necessarily have any causal relationship with the product under investigation.

SAE

An SAE is any untoward medical occurrence that at any dose:

- results in death
- is life-threatening (Note: the term “life-threatening” refers to an event in which the subject is at risk of death at the time of the event; it does not refer to an event which hypothetically may cause death if it is more severe)
- requires subject hospitalisation or prolongation of existing hospitalisation (for the purpose of this study, a hospitalisation is defined as a hospital stay of at least 8 hours and/or an overnight stay)
- results in persistent or significant disability/incapacity
- is a congenital anomaly/birth defect

or

- other medically important condition

Events that require intervention to prevent one or more of the outcomes listed in the definition above are also to be considered as serious. Examples of such events are intensive

treatment in an emergency room or at home for allergic bronchospasm, blood dyscrasias or convulsion that does not result in hospitalisation, or development of drug dependency or drug abuse.

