6.2 Time Point Algorithms

6.2.1 Study Day

The date of first dose of study drug administration during the double blind phase will be considered study day 1, and the day before the first dose of study drug of double blind phase will be study day -1. Study days will be calculated only when the full assessment date is known (i.e., partial dates will have missing study days).

$$\text{Study Day} = \begin{cases} \text{Date of Assessment} - \text{Date of Randomization Visit} + 1 \\ \text{For assessment on or after the day of randomization} \\ \\ \text{Date of Assessment} - \text{Date of Randomization Visit} \\ \text{For assessment before the day of randomization} \end{cases}$$

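### The follow-up call is timed from randomization in Protocol Table 2 and SAP Table 3 but from end of treatment in the Protocol 6.6.1 visit description; only the second matches the 14-day AE collection period, and the passages need reconciling.

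*Protocol*

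**What the plan says.** **Collection period.** The footnote to Protocol Table 2 has AEs collected "from the date of informed consent to 14 days after the final dose of the study drug" and ties that span to the drug's half-life. Protocol 6.6.2.4 repeats the period and accepts events "regardless of whether they are reported by the subject, elicited by investigator questioning, detected through physical examination, or by other means".

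**Call timed from randomization.** Protocol 6.1 says that subjects "will have a follow-up telephone visit at Week 26". Protocol Table 2 gives Week 26 with a +14-day window. SAP Table 3 turns this into study days: scheduled Day 182, window Days 182–196, in a column presented as the protocol's own visit window. SAP 6.2.1 counts study days from the randomization visit.

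**Call timed from end of treatment.** The follow-up entry in Protocol 6.6.1 says: "Two weeks after end of treatment, a telephone follow-up visit will take place". Its heading combines the two: "Follow-up Visit (Week 26 plus 14 days following completion / Early termination of double-blind treatment period". That heading covers early terminators as well as completers.

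**Visit 6.** The Protocol 6.6.1 heading is "Treatment Visit 6 (Week 24 plus/minus 7 days of treatment/Early termination visit: date of discontinuation* plus 7 days". SAP Table 3 gives Days 161–175 for the Week 24 visit.

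**The concern.** The call is the only scheduled contact after Visit 6. Protocol 6.6.1 makes Visit 6 the final collection of the subject diary, so hypoglycaemia after treatment is asked about on a schedule only at this call. So is concomitant treatment, which Protocol 6.5 restricts until two weeks after the final dose.

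The AE period moves with the final dose, while the window in the two schedule tables is fixed to randomization. When Visit 6 is late in its own window, the distance between them shrinks. A site working from the tables could then make the one scheduled enquiry before the period has closed. When treatment ends early, the fixed window bears no relation to the period at all. SAP 4.2 relies on the two weeks as enough to confirm safety after treatment, so the timing of the call should support that statement.

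**Working it through.** **Inputs.** Visit 6 is at Week 24 ± 7 days (Protocol Table 2). The call is at Week 26 + 14 days (Protocol Table 2). AE collection ends 14 days after the final dose (Protocol Table 2 footnote; 6.6.2.4).

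**Reproducing SAP Table 3.** Visit 6: 24 × 7 = 168, ± 7 gives Days 161–175. Call: 26 × 7 = 182, + 14 gives Days 182–196. Both agree with the SAP.

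**Assumption.** The final dose is taken on the day of Visit 6. If it was the day before, every gap from final dose to call is one day longer.

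**Gap under the tables.** Gap = call day − Visit 6 day.

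**Window under the visit description.** The earliest call is Visit 6 + 14. If the +14-day tolerance in the heading also runs from end of treatment, the latest is Visit 6 + 28.

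| Visit 6 | Gap to an in-window call (Days 182–196) | Visit 6 + 14 to + 28 | Call days meeting both |
|---|---|---|---|
| Day 161 | 21 to 35 days | Days 175–189 | 182–189 (8 days) |
| Day 168 | 14 to 28 days | Days 182–196 | 182–196 (15 days) |
| Day 175 | 7 to 21 days | Days 189–203 | 189–196 (8 days) |

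**When an in-window call can be too early.** 182 − Visit 6 day < 14 requires Visit 6 after Day 168, that is Days 169–175, which are 7 of the 15 permitted days. A Day 182 call then comes 13 days (Visit 6 on Day 169) down to 7 days (Day 175) after Visit 6. With the final dose on the day before, Day 169 gives 182 − 168 = 14 and drops out, leaving Days 170–175 with gaps of 13 down to 8 days.

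**When a call at exactly two weeks is out of window.** Visit 6 day + 14 < 182 requires Visit 6 before Day 168, that is Days 161–167. The call would fall on Days 175–181, before the SAP window opens.

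**Can both rules be met?** For Visit 6 on day d up to 168, the overlap runs from Day 182 to d + 28, which is d − 153 days. From 168 onwards it runs from d + 14 to Day 196, which is 183 − d days. The smallest values are 161 − 153 = 8 and 183 − 175 = 8. So every Visit 6 day leaves at least 8 call days that satisfy both.

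**Early terminators.** Suppose treatment ends on Day 56. Two weeks later is Day 70. The Week 8 window closes on Day 63 and the Week 12 window opens on Day 77, so Day 70 lies in no SAP window. Waiting for Day 182 would mean a call 182 − 56 = 126 days after treatment.

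**Illustrative frequency.** If Visit 6 and call dates were spread evenly and independently over their 15-day windows, the combinations with a gap under 14 days number 7 + 6 + 5 + 4 + 3 + 2 + 1 = 28 of 15 × 15 = 225, or 12.4%. That is about 30 of 240 subjects if all complete. It further assumes that sites follow the tables and disregard the visit description.

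**The case against.** The strongest reply is that the protocol, read as a whole, does not permit a day-7 call. The visit description is the instruction that sites work from, and it sets the call two weeks after end of treatment. The explicit Days 182–196 appear only in the SAP, where SAP 6.2.2 introduces them as analysis windows. They matter little there: the call collects only AEs, hypoglycaemia and concomitant medication, and SAP 6.8.1.1 defines treatment-emergent events by onset, not by visit window. Protocol 6.6.2.4 also requires AEs through day 14 to be recorded however they come to light, so a site that called on day 7 and ignored later reports would breach that duty.

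Most of this stands. A reader might infer that the plan leaves days 8–14 with no contact, that the stated follow-up is not delivered, or that the two timings cannot both be met. The documents support none of these. What is missing in the early-call case is a later *scheduled* contact, and that case arises only if the tables are read without the visit description. The timings conflict outright only if the call must be made at exactly two weeks; with the tolerance counted from end of treatment they always overlap.

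The reply does not remove the inconsistency. Protocol 6.1 and Table 2 state Week 26 without reference to end of treatment, the heading of the visit description mixes both anchors, and the SAP presents its day range as the protocol's window. A Day 182 call after a Day 175 visit would be in window by both tables and contrary to the visit description. The SAP row also has no workable meaning for early terminators.

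**Conclusion.** The point holds as an internal inconsistency about when the only scheduled post-treatment contact takes place. Under Protocol Table 2 and SAP Table 3 alone, Visit 6 on Days 169–175 allows an in-window call 7 to 13 days after that visit, before the 14-day AE period ends and with no later scheduled contact. The Protocol 6.6.1 visit description rules this out. Separately, Days 182–196 do not fit subjects who stop early.

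The gaps assume a final dose on the day of Visit 6. The 12.4% (about 30 subjects) is illustrative only and should not be read as an expected loss; under the visit description the number of early calls is zero. Late calls, up to 35 days after Visit 6 in the tables, lengthen recall but do not lose coverage, because the call asks about everything since the last visit. The primary efficacy analysis is unaffected. The correction is worth making because it is specific and costs almost nothing.

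**What to change.** Use one anchor for the call in Protocol 6.1, Table 2, the 6.6.1 follow-up heading and SAP Table 3: the end of treatment, stated as the final dose, which the AE period already uses. Word it so that the call does not come before the stated 14 days are over, for completers and early terminators alike, and state that the existing +14-day tolerance runs from that point. Naming the final dose matters for early terminators, whose visit may come up to 7 days after the decision to discontinue. In SAP Table 3, replace the fixed Days 182–196 with a row defined relative to the final dose.

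The cost is wording in the schedule and one SAP table row, with the same number of calls. For Visit 6 on Day 175 the earliest call moves from Day 182 to Day 189 and the latest from Day 196 to Day 203, a shift of 7 days. Across all permitted Visit 6 days the call would fall on Days 175–203.

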6.6.2 Methods of Assessment

6.6.2.1 Primary Efficacy Parameter

HbA1c

This parameter will be measured by taking a blood sample. Blood samples will be collected at the sites and HbA1c will be measured at a central laboratory.

6.6.2.2 Secondary Efficacy Parameters

Glucose (FPG)

This parameter will be measured by taking a blood sample. Blood samples will be collected at the sites and FPG will be measured at a central laboratory.

6.6.2.3 Other Efficacy Parameters

Insulin, C-peptide and glucagon will be taken in a fasting state. Blood samples will be collected at the sites and parameters will be measured at a central laboratory.

Homeostatic model assessment (HOMA)

Homeostatic Model Assessment-Insulin Resistance (HOMA-IR) and HOMA- β will be evaluated by fasting glucose and fasting insulin as follows:

$$\text{HOMA-IR} = \text{fasting insulin (mU/L)} * \text{fasting glucose (mg/dL)} / 405$$

$$\text{HOMA-}\beta = 360 * \text{fasting insulin (mU/L)} / (\text{fasting glucose (mg/dL)} - 63)$$

Body weight

Body weight will be measured at the beginning of the respective visits.

6.6.2.4 Safety Parameters

Laboratory Monitoring

In addition to the above mentioned special diabetes-related measurements, blood samples will be collected and sent to the central laboratory according to the local procedure for evaluation.

Clinical laboratory parameters to be measured include:

- haematology: haemoglobin, haematocrit, red blood cell count, white blood cell count (with differential in %), platelet count
- blood chemistry: AST, ALT, gamma-glutamyltransferase (GGT), lactate dehydrogenase (LDH), alkaline phosphatase, total bilirubin, total cholesterol, triglycerides, low-density lipoprotein cholesterol (LDL-C), high-density lipoprotein cholesterol (HDL-C), blood urea nitrogen, creatinine, uric acid, total protein, albumin, albumin/globulin ratio, direct bilirubin, creatine kinase, sodium, potassium, chloride, calcium, phosphate, and magnesium
- Pregnancy tests will also be done as serum test at the beginning and the end of study in women with childbearing potential
- Urinalysis will be done via dipstick test and includes sugar, protein, occult blood, urobilinogen, ketone bodies, and pH.

Any clinically significant change observed at each visit in comparison with baseline has to be evaluated carefully and a relationship with a possible cause is to be given (test medication or other treatment received or concomitant pathology).

Vital Signs

Vital signs (sitting systolic/diastolic blood pressure, pulse rate and body temperature) will be evaluated by comparison of the results obtained pre- and post-treatment and record in the eCRF.

Any clinically significant change observed at each visit in comparison with baseline has to be evaluated carefully and a relationship with a possible cause is to be given (test medication or other treatment received or concomitant pathology).

Electrocardiogram (ECG)

Standard 12-lead ECGs (I, II, III, aVR, aVL, aVF, V1 - V6) will be evaluated by comparison of the results obtained pre- and post-treatment. PR-interval, RR-interval, QRS-interval, QT-interval, QTc and heart rate will be recorded in the eCRF.

The results of ECG are to be classified as follows:

1. normal
2. abnormal, but not a clinically significant change
3. abnormal, clinically significant change

Any clinically significant change observed at each visit in comparison with baseline has to be evaluated carefully and a relationship with a possible cause is to be given (test medication or other treatment received or concomitant pathology).

Hypoglycaemic episode

The investigator will instruct the subjects to write the subject diary and monitor the blood glucose by glucometer as much as possible when hypoglycaemia occurred. Subjects should visit hospital if hypoglycaemia symptom is not resolved after taking sugar.

Subjects should carry their diary on each visit, the investigator will check the subject diary until last dose and check if hypoglycaemia occurred.

If a suspicious symptom of hypoglycaemia occurred, Investigators should diagnose and record on eCRF as the following criteria:

Patient's hypoglycaemia symptom after taking sugar	
Resolved	Unresolved
Hypoglycaemia	AE

Investigators will classify the event in accordance with the following categories:

- Severe hypoglycaemia: An event requiring assistance of another person to actively administer carbohydrate, glucagon, or other resuscitative actions.
- Documented symptomatic hypoglycaemia: An event during which typical symptoms of hypoglycaemia are accompanied by a measured plasma glucose concentration ≤ 70 mg/dL (3.9 mmol/L).

- Asymptomatic hypoglycaemia: An event not accompanied by typical symptoms of hypoglycaemia but with a measured plasma glucose concentration ≤ 70 mg/dL (3.9 mmol/L).
- Probable symptomatic hypoglycaemia: An event during which symptoms of hypoglycaemia are not accompanied by a plasma glucose determination, but was presumably caused by a plasma glucose concentration ≤ 70 mg/dL (3.9 mmol/L).
- Relative hypoglycaemia: An event during which the person with diabetes reports any of the typical symptoms of hypoglycaemia, and interprets the symptoms as indicative of hypoglycaemia, but with a measured plasma glucose concentration > 70 mg/dL (3.9 mmol/L).

The investigator will collect the following items and record them on the eCRF. The definitions of the items are equivalent to those for AEs.

- Symptom of hypoglycaemia
- Duration (start and end dates and times)
- Severity grade (mild, moderate, severe)
- Investigator causality (relationship to the study product)
- Action taken (change of study medication)
- Action(s) taken other than change of study medication
- Outcome
- Seriousness
- Value of glucose levels measured by glucometer (when hypoglycaemia occurred)
- Time of glucose levels measured by glucometer (when hypoglycaemia occurred)
- Reasons for hypoglycaemia (unknown, no diet or delay of diet, performed intense exercise, others)
- Time of last diet and study medication before hypoglycaemia occurred.

Further details will be outlined in the eCRF manual.

Cardiovascular events

An Event Adjudication Committee (EAC) will be set up to evaluate the cardiovascular events.

Cardiovascular events are defined as below: Death; Myocardial Infarction; Hospitalisation for Unstable Angina; Stroke & Transient Ischaemic Attack (TIA) (fatal & non-fatal); Urgent Revascularisation Procedures; Hospitalisation for Heart Failure

The detailed review procedure will be developed in a booklet prior to initiating the trial.

Adverse Events

All AEs that occur during the study from the signing of informed consent form through to 14 days after the final dose of the study drug are to be collected and reported on the eCRF, regardless of whether they are reported by the subject, elicited by investigator questioning, detected through physical examination, or by other means.

As far as possible, each AE is described by:

- duration (start and end dates)
- severity grade (mild, moderate, severe)
- investigator causality assessment (relationship to the study product)
- action taken (change of study medication)
- outcome
- seriousness

Definitions and Handling of Adverse Events

AE

An AE is any untoward medical occurrence (change in anatomical, physiological, metabolic function, or clinically significant laboratory abnormality) in a subject, which does not necessarily have any causal relationship with the product under investigation.

SAE

An SAE is any untoward medical occurrence that at any dose:

- results in death
- is life-threatening (Note: the term “life-threatening” refers to an event in which the subject is at risk of death at the time of the event; it does not refer to an event which hypothetically may cause death if it is more severe)
- requires subject hospitalisation or prolongation of existing hospitalisation (for the purpose of this study, a hospitalisation is defined as a hospital stay of at least 8 hours and/or an overnight stay)
- results in persistent or significant disability/incapacity
- is a congenital anomaly/birth defect

or

- other medically important condition

Events that require intervention to prevent one or more of the outcomes listed in the definition above are also to be considered as serious. Examples of such events are intensive

treatment in an emergency room or at home for allergic bronchospasm, blood dyscrasias or convulsion that does not result in hospitalisation, or development of drug dependency or drug abuse.

However, medical judgement has to be exercised in deciding whether an event is serious in any other situations considered medically relevant.

The evaluation of the AE as serious or not-serious is made independently of any attribution of causality.

Events NOT considered to be SAEs are those that require:

- treatment, which is elective or pre-planned, for a pre-existing condition that is unrelated to the indication under study and does not worsen
- treatment on an emergency, outpatient basis for an event NOT fulfilling any of the definitions of serious given above and NOT resulting in hospital admission for the purpose of this study, a hospitalisation is defined as a hospital stay of at least 8 hours and/or an overnight stay).

AE severity

AE severity determined by the clinical investigator on the basis of his/her direct observations or the subject's reporting:

- Mild: causes no limitation of usual activities; the subject may experience slight discomfort
- Moderate: causes some limitation of usual activities; the subject may experience annoying discomfort
- Severe: causes inability to carry out usual activities; the subject may experience intolerable discomfort or pain.

AE causality (relationship guide)

Any AE has to be judged for causality (relationship to study medication).

The relationship of an AE to the study product is to be graded on the basis of the following:

• Reasonable possibility	The relationship of the clinical event to the investigational product administration is "related", "possible related", "Possibly not related" or "unassessable" will be regarded as "reasonable possibility".

• No reasonable possibility	The relationship of the clinical event to the investigational product administration is "not related" will be regarded as "no reasonable possibility".

Handling of AEs

If an AE occurs, appropriate diagnostic and therapeutic measures are to be taken and the study product has to be discontinued if appropriate. Follow-up evaluations of the subject are to be performed, whenever possible, until the subject recovers or until the investigator considers the situation to be no longer clinically significant.

If clinically significant laboratory abnormalities appear at Week 24 or Early termination visit, appropriate additional tests may be performed to clarify the nature of any clinically significant laboratory abnormalities that occur. If an abnormal laboratory value or assessment is clearly related to a medically defined diagnosis or syndrome, the diagnosis or syndrome will be recorded on the AE form, not the individual laboratory values. All clinically significant abnormal laboratory results or assessments will be followed until they resolve (return to normal or baseline values) or stabilise, or until they are judged by the Investigator to be no longer clinically significant. Further details will be outlined in the eCRF manual.

AEs are monitored and registered on the AE form of the eCRF at each visit. The AEs caused from the signing of informed consent form through to 14 days after the final dose of the study drug are collected and reported on eCRF. In absence of a specific diagnosis, an individual AE form has to be filled in for each sign or symptom.

Persistent AEs will be entered once in the eCRF until they are resolved or if a new event has to be documented due to deterioration. These AEs will be carefully monitored; further details of monitoring of persistent AEs will be provided in the monitoring plan. If an AE is still not resolved at the end of the study, this will be documented as ongoing.

For recurrent AEs, i.e., AEs of the same nature, but with a different date of onset, an individual AE form has to be completed for each of them.

If the AE is classified as serious, the clinical investigator has also to complete the SAE report form. It is the responsibility of the investigator to send the SAE report form by fax to the Drug Safety Department of the CRO within 24 hours of receipt and to retain the original copy of the form (keeping a photocopy in the Investigator Site File). At the earliest possible date, the SAE report form has to be followed by a detailed report and any documentation that may be available, e.g., hospital case records, autopsy reports, and/or other pertinent documents. All such reports will identify subjects by unique code numbers assigned to the study subjects only, and will not include the subjects' names, personal identification numbers, or addresses.

All the above documents will be sent by fax to the Drug Safety Department of the CRO within 24 hours of receipt. The responsibility for reporting the SAE to local ethics

committees and the respective health authorities are complied with the national regulatory requirements.

Pregnancies

If the subject or the subject's partner is found to be pregnant during the study, and the embryo-foetus may potentially be exposed to the study medication, the investigator should immediately discontinue the study treatment in the relevant subject and report to the Sponsor accordingly. If the subject wishes to give birth to the child, the investigator will follow up the subject until delivery as far as possible in order to investigate the presence/absence of impact of the study medication on the born baby. Information obtained from the investigation will be reported in writing to the sponsor in the same way as a significant AE.

